9.5 Pregnancy

Any pregnancy that occurs during study participation must be reported to the sponsor/principal investigator. To ensure the safety of the subject, every pregnancy must be reported immediately at the sponsor /experimenter principal. A pregnancy needs to to be followed to determine the outcome (including premature termination) and the status of the mother and baby. The complications from the pregnancy And the interruptions elective For reasons doctors they must to be reported as AE / ADE or SAE. Spontaneous abortions they must be reported as SAE.

Any SAE That Yes check in Association with a pregnancy, scope to your attention of the experimenter after the subject has completed the study and considered by the experimenter as possibly related to the product in study, needs to to be promptly reported at the sponsor/ experimenter principal.

Documento Studio WOUND-H Valutazione prestazioni e sicurezza [acido ialuronico lineare per il trattamento delle ferite]	Codice NA-01-23	v. 2 del 26 giugno, 2023	 NOVA ARGENTIA
--	---------------------------	--------------------------	---

9.6 Severity of the events adverse/effects adverse of the device

The severity of AEs/ADEs is classified on a three-point scale: mild, moderate, severe and reported on a specific section of the CRF.

If the severity of an AE/ADE worsens during administration of a medical device, only the worst intensity must be reported on the AE page. If the AE decreases in intensity, it is not necessary no change in severity.

Mild

The event can to be obvious to the subject; Not influence the activity daily; the AE/ADE Yes solves spontaneously or can request a therapeutic intervention minimum;

Moderate

The event can put to unease The subject; the progress from the activity daily can to be influenced; can be necessary a intervention; the AE/ADE does not produce sequelae.

Serious

The event can cause considerable discomfort; usually interferes with daily activities; the subject you may not be able to continue studying; AE/ADE produces sequelae, which require a intervention prolonged therapeutic.

A AE/ADE light, moderate or serious can or Not can to be serious. These terms I am used For to describe the intensity of a specific event (as in mild, moderate or severe myocardial infarction). However, a serious event may have relatively minor medical significance (such as a severe headache) or otherwise And necessarily serious. To example, there nausea That tough different hours can to be classified as serious, but it may not be clinically important. Fever of 39°C which is not considered serious can become serious if it prolongs hospital discharge by one day. The clinical importance rather than there severity it works from guide to define obligations regulatory Of report.

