9.1 Events adverse

The events adverse due to use Of acid hyaluronic In the treatment from the wounds I am generally traceable to phenomena Of intolerance to the product And solvable in few days without treatment.

Everyone The events adverse insurgents during The treatment, right away After The treatment And In the period Of follow up will be recorded in the “Adverse Event Form” (Annex I of the CRF). Adverse events will come classified by severity, relationship with the device being studied, intended or not, need Of treatment.

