9.8 Procedures Of report

A section special And dedicated to AE/ADE In the CRF. They have to Therefore to be inserted the following data:

- Type of AE/ADE
- Start (date And Now)
- end (date And Now)
- Severity (mild, moderate, serious)
- Serious (no Yes)
- Unexpected (no / Yes)
- Outcome (Resolved, in course, in course – improved, in course – worsening)
- Relationship with the medical device (unrelated, possibly related, definitely related) The events adverse related to the device they must to be documented In the CRF in compliance with the criteria above mentioned e reported to the Sponsor.

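### The severity grades in 9.6 mix intensity with sequelae, so an intense reaction that resolves fits two grades; separately, the outcome list in 9.8 has no code for death or recovery with sequelae

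*Combined protocol and SAP*

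**What the plan says.** Section 9.6 sets up the grading: "The severity of AEs/ADEs is classified on a three-point scale: mild, moderate, severe". For moderate, the closing descriptors are that it "can be necessary a intervention; the AE/ADE does not produce sequelae". For the top grade they begin "The event can cause considerable discomfort; usually interferes with daily activities" and end "AE/ADE produces sequelae, which require a intervention prolonged therapeutic".

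The same section then explains that the grades describe how intense a given event is, as distinct from whether it is serious in the regulatory sense. As an example, it says "there nausea That tough different hours can to be classified as serious, but it may not be clinically important". It also says that if an event worsens during use of the device, only its worst intensity is reported, and that the grade need not change when the event eases.

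Section 9.8 lists the CRF fields for each event. Severity, seriousness and outcome are separate fields. The outcome field reads "Outcome (Resolved, in course, in course – improved, in course – worsening".

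Section 9.1 describes reactions to hyaluronic acid in wounds as "generally traceable to phenomena Of intolerance to the product And solvable in few days without treatment".

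**The concern.** A severity scale should let two investigators who see the same event give the same grade. Here the boundary between moderate and the top grade uses two different ideas: how intense the event is, and what it leaves behind. Sequelae are an outcome, yet they appear in the severity definitions and are absent from the outcome list.

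Safety is part of the primary objective in section 4, and sections 9.1 and 9.2 require every adverse event to be classified by severity. Section 5.6 assesses safety descriptively, with no test, so its value depends on the coding being coherent. If grading varies between assessors, or a death or lasting effect has no correct code, a comparison of the arms on severity or outcome cannot be read with confidence.

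**Working it through.** No arithmetic applies, and the plan gives no figure on this point to reproduce. The check is to set the passages side by side and put test cases through them.

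**Severity (9.6).** Take a local reaction that causes considerable discomfort, interferes with daily activities for a few days, and then clears completely.

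| Text in 9.6 | Does the event fit? | Grade indicated |
|---|---|---|
| Moderate: discomfort, daily activity may be affected | Yes | Moderate |
| Moderate: "the AE/ADE does not produce sequelae" | Yes | Moderate |
| Top grade: "The event can cause considerable discomfort; usually interferes with daily activities" | Yes | Top |
| Top grade: "AE/ADE produces sequelae, which require a intervention prolonged therapeutic" | No | Not top, if all descriptors are required |
| Statement that grades describe intensity | Yes, it was intense | Top |
| Nausea example, with no sequelae mentioned | Comparable | Top |

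The result depends on a rule that the section does not give:

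1. If all descriptors must be met, the event is moderate.
2. If any one is enough, it fits both grades.
3. If intensity governs, as the explanatory text says, it belongs in the top grade.

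The opposite case fails as well. An event of low intensity that leaves a lasting effect is mild on intensity, is shut out of moderate by the no-sequelae clause, and meets one descriptor of the top grade. The error therefore has no fixed direction.

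The worst-intensity rule does not settle the matter. It keeps the highest grade reached, but does not say how a grade is assigned. It also adds a problem of timing: peak intensity is known at the peak, whereas sequelae are known only afterwards.

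**Outcome (9.8).** Put each possible end state against the four codes.

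| End state | Correct code in 9.8 | Recorded elsewhere? |
|---|---|---|
| Full recovery | Resolved | – |
| Still present, unchanged, better or worse | One of the three ongoing codes | – |
| Recovery with sequelae, serious event | None | Written report, 9.9 |
| Recovery with sequelae, non-serious event | None | No coded place |
| Death | None | Written report, 9.9 |

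The serious-event criteria (set out within 9.2) include death and permanent impairment, so the plan foresees both. Under 9.9 the written report describes the outcome, and a follow-up report covers it again. That information is not lost, but the coded field would be blank or wrong. Nor can the field be used to check the sequelae descriptor on which 9.6 partly relies.

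The two defects are independent: a missing outcome code does not itself change a severity grade.

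**The case against.** The strongest reply is that 9.6 lists descriptors without calling them cumulative, and that its intensity statement and nausea example show that the top grade is open to events without sequelae. The text also reads as a rough translation, so a contrast between flat and hedged verbs should not carry much weight. Both points stand. A reader might infer that the top grade is closed to events without sequelae, so that expected reactions could never be severe and intense reactions would be systematically graded down. The documents do not support that. It follows only if every descriptor is required, and 9.1 says that reactions generally, not always, resolve quickly. What remains is a contradiction that permits either grade.

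A second reply is that little depends on the boundary. Section 5.6 names only the rate of adverse reactions and the occurrence of reactions not described in the literature, and no severity table is planned. Section 9.6 ties regulatory reporting to clinical importance rather than to severity. This also stands, and it limits the consequence. It does not remove the requirement to grade every event.

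A third reply is that the CRF may hold more than 9.8 lists. Sections 9.1 and 9.2 classify events by need for treatment, which 9.8 omits, and the Adverse Event Form (Annex I of the CRF) is not among the documents. That is possible, and the form should be checked. As written, though, 9.8 presents its outcome list as the set of categories.

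**Conclusion.** Wrong as written, with limited reach. Section 9.6 contradicts itself at the boundary between moderate and the top grade, and an intense event that resolves fully can be given either grade. Severity classification therefore cannot be expected to be consistent. Separately, 9.8 has no correct code for two outcomes, death and recovery with sequelae; for sequelae of non-serious events there is no coded place at all.

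The number of events affected cannot be estimated, because the documents give no expected rate of adverse events or their grades. No efficacy endpoint, sample-size figure or specified test changes, and regulatory reporting does not depend on the grade. It would go too far to say that the plan cannot record deaths or lasting harm: the written report under 9.9 covers the serious cases.

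The conclusion assumes that the translated text reflects the source wording on sequelae, and that the CRF follows the list in 9.8.

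**What to change.** - In 9.6, remove the sequelae clauses from the moderate and top-grade definitions, so that severity is graded on intensity and interference with daily activity, as the section itself states.
- In 9.8 and the CRF, add *resolved with sequelae* and *fatal* to the outcome list.
- In the safety analysis, summarise severity and outcome separately by arm.

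The cost is a wording change in the protocol and CRF, and two extra codes. The downside is that more events may appear in the top grade.

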9.7 Relation with The device doctor

For all, the investigator will evaluate the causal relationship between the medical device and the AE/ADE using there her experience clinic And The his judgment second The following algorithm That Better Yes suitableat circumstances of the EA / ADE:

Not related

- Can follow or less a sequence storm reasonable from the administration of the product in study
- AND biologically Not plausible And Not follows a model Of answer known to the device doctor (self The model Of answer And previously known)
- Can to be explained give her characteristics Note of the state clinical of the subject or from other mode Of therapy administered to the subject.

Documento Studio WOUND-H Valutazione prestazioni e sicurezza [acido ialuronico lineare per il trattamento delle ferite]	Codice NA-01-23		
v. 2 del 26 giugno, 2023			

Possibly related

- Continued a reasonable sequence storm from the administration of the device doctor.
- Can follow a model Of answer known to the device doctor (self The model Of answer And previously known).
- Could be Not to be reasonable Not to be reasonably explained give her characteristics Note of the state clinical of the subject or from other mode Of therapy administered to the subject, self applicable.

Surely related

- Continued a reasonable sequence storm from the administration of the device doctor.
- Continued a model Of answer known to the device doctor (self The model Of answer And known inprecedence).
- Not And present no one else cause reasonable.

9.8 Procedures Of report

A section special And dedicated to AE/ADE In the CRF. They have to Therefore to be inserted the following data:

- Type of AE/ADE
- Start (date And Now)
- end (date And Now)
- Severity (mild, moderate, serious)
- Serious (no Yes)
- Unexpected (no / Yes)
- Outcome (Resolved, in course, in course – improved, in course – worsening)
- Relationship with the medical device (unrelated, possibly related, definitely related) The events adverse related to the device they must to be documented In the CRF in compliance with the criteria above mentioned e reported to the Sponsor.

9.9 Procedures Of report For SAE/SADE

In case Of event adverse serious (serious adverse event), the experimenter needs to use all the measures support for the best treatment of the patient. A written report must also be prepared And mass immediately to disposition of the sponsor. They should to be available at least the following details:

- Initials And code of the patient
- Patient: date Of birth, sex, origin ethics
- The device doctor used
- The event adverse valued as serious
- Brief description of the event And of the outcome

Documento Studio WOUND-H Valutazione prestazioni e sicurezza [acido ialuronico lineare per il trattamento delle ferite]	Codice NA-01-23		
v. 2 del 26 giugno, 2023			

- Self related or Not related to the device

There relation written And split in two set off:

- Relationship initial: in shape on that is That And happened (AE / HADES valued as serious), self exists arelation with the medical device ... And Which action And was set.
- Follow-up Report: in shape on the outcome

The Sponsor is responsible for the classification of adverse events and the ongoing evaluation of the safety of the investigation clinic And needs to:

- to review there assessment of the experimenters Of everyone The events adverse And to determine And to document For recorded their severity and relationship with the investigation device; in case of disagreement between the sponsor and the experimenter principal
- to examine all the shortcomings of the devices And to determine And to document For signed up self they would have could bring to a serious effect adverse of the device; in case Of disagreement Between the sponsor And the experimenterprincipal
- report or guarantee there report, to the THERE IS And to the AR (Ministry from the Health) Of everyone The events adverseserious.

10 Withdraw of the patients give it study

10.1 Criteria For The withdraw of the subjects give it study

THE subjects can to interrupt prematurely the investigation clinic in any moment. The interruption premature study is to be understood when the subject has not been subjected to evaluation safety it's at all the clinical evaluations during the investigation clinic.

THE subjects they must to be retreat in following circumstances:

- on own request
- self the investigator believes That Not would be In the improve interest of the subject to continue
- self The subject viola the conditions established In the module Of consent / form information or ignore theinstructions receipts.
- self arise events adverse serious such from to compromise there assessment clinic.

In everyone the cases, The reason For which the subjects they come retreat needs to to be registered in detail in the CRF And in the subject's medical records. If the clinical investigation is terminated prematurely, all of the material of the investigation clinic (CRF complete, partially completed And empty) will be preserved.

Documento Studio WOUND-H Valutazione prestazioni e sicurezza [acido ialuronico lineare per il trattamento delle ferite]	Codice NA-01-23		
v. 2 del 26 giugno, 2023			

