10.2 Follow up of the patients retreat from the investigation clinic

In case Of break premature After The treatment with The device doctor, the investigations expected For there assessment from the safety they will be performed 7 days After the interruption. THE subjects they will be informed that participation in these investigations is voluntary. Furthermore, they can ask that from the moment of withdraw no more data is recorded.

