10.3 Politics Of replacement of the subjects retreat

THE subjects That Yes they withdraw give it study Before from the execution from the procedure surgical or immediately after, i.e. before visit 2 (7 days after treatment) they may be replaced by new subjects who meet the inclusion/exclusion criteria. Those who withdraw give it study after visit 2 will be included in the analysis.

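### Patients removed from the study after certain serious adverse events, or by the investigator, have no healing assessment scheduled, so outcome-related data can be lost

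*Combined protocol and SAP*

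**What the plan says.** The text is a machine translation, but the operative clauses can be followed.

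- **Removal is mandatory and is from the study.** Section 10.1 introduces its list with "THE subjects they must to be retreat in following circumstances". The list includes SAEs that compromise the clinical assessment ("self arise events adverse serious such from to compromise there assessment clinic") and the investigator's view that continuing is not in the patient's interest ("self the investigator believes That Not would be In the improve interest of the subject to continue"). Section 5.2 separately excludes a patient from the study when an SAE prejudices continuation.
- **Visit 4 procedures.** Section 5.2 asks for them when the patient chooses to leave. The exclusion rule comes in the next sentence and carries no such request.
- **Follow-up after withdrawal.** Section 10.2 provides that "the investigations expected For there assessment from the safety they will be performed 7 days After the interruption" and tells patients "that participation in these investigations is voluntary". It adds that they may ask for no further data to be recorded.
- **Analysis.** Section 10.3 lets patients who leave before visit 2 be replaced. For later withdrawals: "Those who withdraw give it study after visit 2 will be included in the analysis".
- **Endpoints.** Section 5.6 makes the visit 3 Clinical Healing score and the visit 4 wound size primary, and the visit 4 healed percentage secondary. Section 15 gives no rule for missing values.
- **Reason for withdrawal.** Section 10.1 requires it: "The reason For which the subjects they come retreat needs to to be registered in detail in the CRF".

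**The concern.** Stopping a device and leaving a trial are different events. A patient whose wound fails badly enough to end gel treatment still has a wound that can usually be graded, measured and called healed or not healed. The lowest grade of the Clinical Healing Score (scheme in section 5) even lists infection with suppuration. If that patient is taken out of the study and nobody is told to see the wound at visits 3 and 4, the poor result may never be recorded.

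The loss arises after randomisation and can depend on the outcome, so randomisation does not protect the comparison. Both primary endpoints and the healed percentage are exposed. Safety reporting is not: sections 9.8 and 9.9 still require adverse events and SAEs to be recorded and reported.

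**Working it through.** **1. Does any clause secure a healing outcome for a patient removed under the SAE or investigator rule?**

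| Clause | What it gives | Healing outcome secured? |
|---|---|---|
| 5.2, visit 4 request | Visit 4 procedures after the patient's own withdrawal | No; and even where it applies it does not secure the visit 3 score |
| 9.9, SAE follow-up report | Outcome of the SAE | No |
| 10.2, 7-day checks | Voluntary safety investigations | No |
| 10.2, opt-out | Implies recording may otherwise continue | No; it schedules no healing visit |
| 10.3, before visit 2 | Replacement allowed | No |
| 10.3, after visit 2 | Inclusion in the analysis | No; a patient removed between visits 2 and 3 has no visit 3 or visit 4 values to include |

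**2. The plan's own numbers (section 14).** 53 per group is 106; 106 / 0.95 = 111.6, rounded up to 112, or 56 per arm. This reproduces. The 5% dropout allowance is 0.05 × 112 = 5.6 patients from all causes.

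**3. Healed percentage.** Assumptions, none of them in the documents: k = 1 or 2 such patients in an arm of 56; a proportion p of the assessed patients healed; none of the k wounds healed; the k patients left out of numerator and denominator. The rate over all 56 is p(56 − k)/56, so leaving the k out overstates the arm by pk/56.

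| p | k = 1 | k = 2 |
|---|---|---|
| 60% | 1.1 points | 2.1 points |
| 80% | 1.4 points (80.0% v 78.6%) | 2.9 points (80.0% v 77.1%) |
| 90% | 1.6 points | 3.2 points |

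If one of two missing wounds is in fact healed, the true rate is (54p + 1)/56. The overstatement is then 0.4, 1.1 and 1.4 points at p = 60%, 80% and 90%.

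**4. Visit 3 score.** Assume five ordered grades with control shares of 5/20/40/27/8% (grades 1 to 5), cut from a normal variable, with the device arm shifted by the plan's 0.5 SD. The probability that a device patient does better than a control patient, ties counted half, is θ = 0.627 with the patients left out. Now give the missing patients a common worst rank, with a = (device count)/56 and b = (control count)/56:

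P = (1 − a)(1 − b)θ + (1 − a)b + ab/2

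| Missing, device v control | P |
|---|---|
| 1 v 0 | 0.616 |
| 2 v 0 | 0.604 |
| 1 v 1 | 0.622 |
| 0 v 1 | 0.633 |
| 0 v 2 | 0.640 |

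Leaving patients out flatters the device when it has more of these events and penalises it when control has more. Equal counts still move P a little, from 0.627 to 0.622, so unequal counts are the main source of bias but not the only one.

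**5. Scale against sampling error.** The standard error of the healed difference at 80% in both arms is √(2 × 0.8 × 0.2 / 56) = 7.6 points. The null standard error of P is √(113 / (12 × 56 × 56)) = 0.055. With events in one arm only, one patient shifts the healed difference by 1.4/7.6 and P (1 v 0) by 0.011/0.055, each about 0.2 standard errors. Two patients shift them by 2.9/7.6 and (2 v 0) 0.023/0.055, each about 0.4.

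**6. Wound size.** The documents give no basis for a figure.

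**The case against.** The strongest reply is that the plan is silent rather than wrong.

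- **Section 10.3 may already protect the healed percentage.** If withdrawals after visit 2 stay in the denominator and are not counted as healed, the overstatement is zero. This stands. A reader might infer that the healed percentage will be too high, but that needs these patients to be left out, which the plan does not say.
- **Section 10.1 may not stop the visits.** It describes premature interruption as arising "when the subject has not been subjected to evaluation safety it's at all the clinical evaluations during the investigation clinic". A reader might take this as an instruction to end healing assessments. It is a garbled definition of who counts as interrupted, and it does not tell staff to stop. The point rests instead on mandatory removal combined with the absence of any scheduled healing visit.
- **Recording may continue.** The opt-out in section 10.2 suggests so. That is fair, but permission to record does not schedule an assessment.
- **Few patients may be affected.** Neither SAE trigger names the wound, and an infected wound can still be graded. Only some of these SAEs will be wound failures. This stands and keeps the point small.
- **Visits cannot rescue an assessment that the SAE has compromised.** This is partly true: a patient who is reoperated or transferred may be seen late or not at all. Other patients removed under these rules can still be assessed.

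Nor do the documents support a claim that the bias favours the device. Its direction depends on which arm has more such events.

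**Conclusion.** The gap is real: these rules take patients out of the study, and nothing in the plan arranges for their wounds to be assessed afterwards. Where the trigger is a wound failure, data can be lost for a reason tied to the outcome. Patients removed before visit 2 may also be replaced, and the plan does not say that they stay in the analysis.

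The size is modest. With one or two such patients in an arm, the distortion is about 0.2 to 0.4 standard errors on the healed difference or the visit 3 comparison. That rests on assumed counts, healed rates and grade shares, on poor outcomes in the missing patients, and on their being left out. This is a worthwhile, inexpensive improvement. It is not a threat to the trial's conclusions on its own.

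**What to change.** - **Sections 5.2 and 10.1:** state that an SAE or an investigator decision may stop the device, but that visits 3 and 4 take place as scheduled unless the patient withdraws consent, and that the observed score, wound size and healed status are used.
- **Section 5.2:** extend the existing request for visit 4 procedures to withdrawals made by the investigator.
- **Section 10.3:** keep every randomised patient in the analysis set, including those who leave before visit 2, whether or not they are replaced.
- **Section 15, optional:** add a sensitivity analysis that counts a wound as not healed when a wound SAE makes it impossible to assess, applied identically in both arms. This is one choice among several. The reason for withdrawal already recorded in the CRF should identify these patients.

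The cost is a few sentences and a little more follow-up effort. No new visits are needed, because visits 3 and 4 already exist. Healing rates may come out slightly less favourable, and some reoperated or transferred patients will still not be assessable.
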